8.3.1. Time Period and Frequency for Collecting AE and SAE Information

All SAEs and AEs will be collected by the investigator from the time of signing the informed consent through the Day 265 visit or for 28 days after the last study treatment for those who early terminate. For subjects who undergo the screening biopsy and are not subsequently dosed, AEs will be followed for 28 days after the biopsy. This will include any AEs that are ongoing at the time of completion/termination of the study. All ongoing AEs must be followed until resolution or for 28 days after the subject's last study treatment, whichever comes first.

All SAEs will be recorded and reported to the sponsor or designee within 24 hours, as indicated in Section 10.3. The investigator will submit any updated SAE data to the sponsor within 24 hours of it being available.

Investigators are not obligated to actively seek AEs and SAEs after conclusion of subject study participation. However, if the investigator learns of any SAE, including death, at any time after the subject has been discharged from the study, and the investigator considers the event to be reasonably related to the study treatment or study participation, including all medically significant and grade 4 labs, the investigator must promptly notify the sponsor.

The method of recording, evaluating, and assessing causality of AEs and SAEs and the procedures for completing and submitting SAE reports are provided in Section 10.3.

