4.6.1.1. Treatment Emergent Adverse Events

TEAEs are defined as any AEs that occur or worsen (increase in severity) on the same day or after the study drug administration on Day 1.

Refer to Section [6.3.1.2](#) to identify TEAE status when start date of an AE is unknown.

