4.6.1.3. Relationship to Study Drug

Causal relationship of an AE with study drug will be classified by the investigator and will be reported as “Not related”, “Unlikely related”, “Probably related” or “Possibly related”. The sponsor will classify “Probably related” and “Possibly related” causality assessments as positive causality and “Not related” and “Unlikely related” causality assessments as negative causality.

Any missing relationship of an AE to study drug will be considered as related to study drug for the analyses, following worst case principle.

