6.2. Derived Variables

Refer to Table 12 below for derived variables and their definitions for various study parameters.

Table 12: Derived Variables and Definition

Variable	Definition
Height (cm)	If height is recorded in inches, then height is equal to the recorded value multiplied by 2.54 and then rounded to 1 decimal place.
Weight (kg)	If weight is recorded in pounds, then weight is equal to the recorded value multiplied by 0.454 and then rounded to 1 decimal place.
Baseline	Baseline is defined as the last non-missing measurement/assessment prior to the CCH injections given at Day 1. Any assessments performed at an unscheduled visit will be considered in the calculation of baseline, if the unscheduled assessment is the closest value preceding the study drug injection.
Study Day	Study Day will be computed as Date of Assessment – Date of Day 1 + 1 for assessments on or after Day 1, else study day will be computed as Date of Assessment – Date of Day 1.
Change from Baseline	Change from baseline will be derived as post-baseline visit/time point value – the baseline value.
Last Date in the Study	Last date in study is defined as: 
 • The date of Day 265 (Biopsy follow-up visit) if the subject completes the study • The date of early termination visit if the subject is terminated early from study at a non-scheduled visit • The date of the latest scheduled visit if the subject is terminated early from study at a scheduled visit or lost to follow-up.
Age (Years) at EFP Symptom Onset	Date of EFP symptoms reported – Date of Birth/365.25. See Section 6.3.1.3 for handling of partial or unknown EFP symptom onset dates.
Time (Years) Since Last EFP Treatment	Date of most recent EFP treatment – Date of informed consent/365.25. See Section 6.3.1.3 for handling of partial or unknown EFP treatment dates.
Duration (Minutes) of Exposure at Each Visit	Date/Time of Last Injection – Date/Time of First Injection
Duration of AE(Days)	AE end date – AE start date + 1
AE Onset Day	AE start date – Date of Day 1 + 1.

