6.3. Handling of Missing Data

Subjects who discontinue the study any time after the initiation of the study drug will not be replaced and available data of these subjects until the point of discontinuation will be summarized. The missing baseline assessment will not be imputed.

For categorical variables with missing values, a category documenting the frequency of missing values will be displayed in the summary tables.

Subjects who discontinue early will be encouraged to complete all end of study (EOS) procedures and assessments at an early termination visit.

There will be no imputation of missing values for safety data, however missing relationship between AE and study drug will be considered as related to study drug following worst case principle. Missing severity of an AE will be summarized as a severe AE.

Immunogenicity samples with a positive titer value will undergo a log transformation for analyses. Samples with titer levels less than 1 will be assigned or imputed as a log transformed titer of 0 for analyses.

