6.3.1.2. TEAE Status When Start Date Is Unknown

The following rules will apply in cases where start date of an AE is unknown:

- If the AE onset date is unknown and the end date is after the date of CCH injection on Day 1 or ongoing, then the AE will be considered a TEAE.
- If the AE onset date is unknown and the end date is before the date of CCH injection on Day 1, then the AE will not be considered a TEAE.
- If both the start date and end date are unknown (or ongoing), then the AE will be considered a TEAE, following the worst-case principle.

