7.7.2. Adverse Events

All AE summary tables will include TEAEs and the AEs before the first injection.

AEs will be summarized by SOC and PT and by treatment region and overall as frequency counts and percentages of subjects with AEs and number of AEs (total events), unless otherwise specified.

A subject will only be counted once per SOC and PT.

For AEs by severity grade (mild, moderate, severe), if a subject has multiple events occurring in the same SOC or same PT, then the event with the maximum intensity (ie, severe) will be counted.

For AEs by relationship to study drug, if a subject has multiple events occurring in the same SOC or same PT, the event with the highest association (ie, related) to study drug will be summarized.

AEs will be presented in decreasing order of the incidences at SOC level and within each SOC, in decreasing order of the incidences at the PT level.

An overall summary of AEs and AEs related to study drug will be presented and will include:

- Any AE.
- Any mild, moderate and severe AE.
- Any study drug related AE.
- Any serious AEs.
- Any study drug related serious AE.
- Any AEs leading to study drug interruption/discontinuation.
- Any study drug related AEs leading to study drug interruption/discontinuation.
- Any AEs leading to study withdrawal.
- Any study drug related AEs leading to study withdrawal.
- Any AEs resulting in death.
- Any study drug related AEs resulting in death.
- Any AESIs.

The following summary tables will be presented by SOC and PT:

- All AEs.
- AEs by Severity.
- TEAEs by Relationship to Study Drug.
- Serious AEs.
- Serious study drug related TEAEs.
- TEAEs leading to study drug interruption/discontinuation.

- Study drug related TEAEs leading to study drug interruption/discontinuation.
- AEs leading to study withdrawal.
- Study drug related TEAEs leading to study withdrawal.
- AEs resulting in death.
- Study drug related TEAEs resulting in death.
- AESIs.

Most common non-serious AEs by order of frequency (most frequent, 2nd most frequent, and 3rd most frequent) will be summarized by PT. Most common non-serious AEs are any PT that at least 5% of the subjects reported at least once.

The following listings will be presented by subject:

- All AEs.
- Serious AEs.
- AEs resulting in drug interruption/discontinuation.
- AEs resulting in study withdrawal.
- AEs resulting in deaths.
- AESIs.

Refer to [Table 12](#) for computation of duration of AEs.

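### The SAP's missing-causality rule has no exposure condition, so a blank field can put a pre-injection AE, or an AE in a never-dosed woman, into the overall drug-related counts

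*SAP*

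**What the plan says.** **Missing causality.** SAP 4.6.1.3: "Any missing relationship of an AE to study drug will be considered as related to study drug for the analyses, following worst case principle". SAP 6.3 says the same: "missing relationship between AE and study drug will be considered as related to study drug following worst case principle". Neither sentence mentions dosing or the timing of the event.

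**Who and what is in the tables.** SAP Section 5 (Table 11) admits to the Safety Population anyone with a screening MRI or biopsy. Protocol 9.2 asks for the screening biopsy. Neither asks for a dose. Protocol 8.3.1 collects AEs in women who are never dosed: "For subjects who undergo the screening biopsy and are not subsequently dosed, AEs will be followed for 28 days after the biopsy". SAP 7.7.2 opens with: "All AE summary tables will include TEAEs and the AEs before the first injection". The overall AE summary in that section has rows for drug-related AEs and drug-related serious AEs, and neither row is limited to TEAEs. The relationship tables by system organ class (SOC) and preferred term (PT) are titled as TEAE tables.

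**TEAE status.** With a known onset, SAP 4.6.1.1 counts AEs that "occur or worsen (increase in severity) on the same day or after the study drug administration on Day 1". With an unknown onset, SAP 6.3.1.2 has three rules. The first makes the event a TEAE: "If the AE onset date is unknown and the end date is after the date of CCH injection on Day 1 or ongoing". The second excludes it if the "end date is before the date of CCH injection on Day 1, then the AE will not be considered a TEAE". The third makes it a TEAE when both dates are unknown, without reference to an injection.

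**Day count.** SAP 6.2 (Table 12) defines AE Onset Day as "AE start date – Date of Day 1 + 1" with no separate branch before dosing. In the same table, Study Day adds 1 only for dates on or after Day 1.

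**The concern.** Worst-case imputation is meant for cases where the answer is uncertain. If an AE is known to have started before the first injection and did not worsen afterwards, or if the woman never received CCH, the drug cannot have caused it. Imputing a drug relationship there is an error, not caution.

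It matters here because every woman who is dosed has a punch biopsy first. Biopsy complications are therefore the obvious kind of pre-injection AE, and safety of CCH is a secondary objective. If a biopsy event with blank causality is counted as drug-related, the overall summary mixes harm from the procedure with harm from the drug. The layout does not help the reader to separate them. Demographics, medications, laboratory and vital-sign summaries (SAP 7.3, 7.5, 7.7.3, 7.7.4) have a group for women not treated, whereas the AE tables are laid out by treatment region and overall only.

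**Working it through.** The plan gives no figure on this point to reproduce. The check is to apply the rules literally to each type of case and then to size one affected subject.

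**1. Blank causality (SAP 4.6.1.3, 6.3, 7.7.2)**

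- Dosed woman, AE known to start before Day 1, no worsening: not a TEAE under 4.6.1.1, but imputed as related. It is in the tables under 7.7.2, so it counts in the overall drug-related row, and in the serious row if serious.
- Never-dosed woman in the Safety Population: same result.
- SOC/PT relationship tables: their TEAE titles would screen out both cases when onset is known, although the opening sentence of 7.7.2 points the other way.

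**2. Unknown onset (SAP 6.3.1.2)**

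| End of AE | Dosed woman | Never-dosed woman |
|---|---|---|
| Before Day 1 | Not a TEAE | Undefined: no injection date |
| On Day 1 | Unclassified: neither after nor before | Undefined: no injection date |
| After Day 1 | TEAE | Undefined: no injection date |
| Ongoing | TEAE | TEAE |
| Unknown | TEAE | TEAE |

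The two TEAE cells in the right-hand column are wrong, because there was no treatment for the event to emerge from. The unclassified cell conflicts with 4.6.1.1, which counts same-day events.

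**3. AE Onset Day (SAP Table 12)**

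For an AE that starts k days before Day 1:

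- AE Onset Day = −k + 1
- Study Day = −k
- Difference = 1 day for every k ≥ 1

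With k = 1, the results are Day 0 and Day −1. With k = 14, they are Day −13 and Day −14, so an AE on the day of a Day −14 biopsy appears to start one day after it. On or after Day 1 the two formulas agree.

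**4. Size of one affected subject**

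Inputs: about 18 screened and about 12 dosed (SAP 3.1). The safety denominator is the SAP Safety Population (SAP 7.7 and Table 11). Assumption: any number from 0 to 18 − 12 = 6 undosed women had a screening MRI or biopsy, so the denominator lies between 12 and 18.

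- Largest: 1/12 = 8.3%
- Smallest: 1/18 = 5.6%
- If the affected woman was herself never dosed, the denominator is at least 12 + 1 = 13, and the largest value is 1/13 = 7.7%.

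These are maxima. The row counts subjects, so it rises only if the woman has no other drug-related AE.

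**5. The rules after the fix**

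Never-dosed women give no TEAEs and no AEs imputed as related. AEs known to predate injection and not to worsen give none imputed as related. In dosed women, an unknown-onset AE that is ongoing, ended after Day 1 or has no end date remains a TEAE, and one that ended on Day 1 becomes a TEAE.

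**The case against.** **Blank fields should be rare.** Protocol 10.3.2 requires relatedness to be stated on a four-point scale that includes a not-related category, and 10.3.4.1 makes the investigator responsible for the assessment. The expected entry for a biopsy event is therefore not-related. A reader might infer that causality is routinely left empty for screening-biopsy events, because the question concerns CCH. The documents do not support that. The example in 10.3.2, where an event from an earlier phase is assessed for active treatment only if it worsens, leaves room for a blank but does not show one. This part of the objection stands: the frequency is unknown.

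**Much of the reporting is protected.** The SOC/PT relationship tables are titled as TEAE tables, and the dated branches of 6.3.1.2 do refer to the Day 1 injection. Treating an unknown-onset ongoing AE as a TEAE in a dosed woman is ordinary conservative practice. A reader might infer that the safety tables as a whole report biopsy harm as CCH harm, but the text supports that clearly only for the overall-summary rows. Protocol 9.3.3.1 limits summaries to TEAEs. That conflict with the SAP is a separate matter, and it does not repair the SAP's rule.

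**The effect may be nil in a dosed woman.** Protocol 2.3 describes injection-site bruising, swelling and pain as common, so she may already be counted as having a drug-related AE. This stands, but it does not help for a never-dosed woman, who has no injection-site reactions. A reader might also take the 19 dosed subjects in Protocol 4.1 or the 6 per region in SAP 3.3 as denominators. These come from different versions of the design, and neither is the SAP's Safety Population.

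**The day-count error is small.** It does not affect TEAE status, and SAP 7.7.2 cites Table 12 only for AE duration. This also stands.

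**Conclusion.** The concern holds as a gap in the SAP's wording. The missing-causality rule in 4.6.1.3 and 6.3 lacks an exposure condition, and the population and table scope that the SAP chose bring unexposed events within its reach. The clear consequence is in the overall-summary rows for drug-related AEs and drug-related serious AEs. One affected subject adds at most 5.6% to 8.3% overall, given the SAP's planned numbers, between 0 and 6 undosed women in the Safety Population, and no other drug-related AE in that subject.

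Two lesser defects are also real. The ongoing branch and the both-dates-unknown rule of 6.3.1.2 reach never-dosed women, and an unknown-onset AE that ended on Day 1 has no class. AE Onset Day disagrees with Study Day by one day for every pre-dose AE.

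Whether any of this will occur cannot be judged from the documents, which do not say how often causality or onset dates are missing. The case for correcting it is that a stated rule can give an impossible answer, in a study small enough for one subject to show, and that the correction is cheap.

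**What to change.** Make four SAP edits before programming:

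1. **4.6.1.3 and 6.3.** Limit the missing-causality imputation to TEAEs in dosed subjects, including pre-dose AEs that worsen after dosing. Treat a missing causality as not drug-related only for AEs in never-dosed subjects, or AEs known to start before the first injection that do not worsen afterwards. Leave every recorded investigator assessment unchanged. The no-worsening condition is needed because 4.6.1.1 counts a pre-dose AE that worsens after dosing as a TEAE.
2. **6.3.1.2, scope.** Restrict the unknown-onset rules to subjects who received CCH.
3. **6.3.1.2, first rule.** Change the end-date condition from after Day 1 to on or after Day 1, in line with 4.6.1.1.
4. **Table 12.** Compute AE Onset Day with the Study Day formula.

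The cost is four short edits and no data. The one downside is slightly less conservative counting of pre-dose AEs with blank causality.

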4.6.2. Potentially Clinically Important Laboratory Values

Potentially clinically important (PCI) laboratory values are presented in Table 9 below.

Table 9: Potentially Clinically Important Laboratory Criteria

Parameter	PCI Low: Less than or equal to	PCI High: Greater than or equal to
Hemoglobin (g/L)	100	190
Hematocrit	0.3	0.6
Platelets (10^9 /L)	100	650
ALT (U/L)		$3 \times \text{ULN}$
AST (U/L)		$3 \times \text{ULN}$
Creatinine ($\mu\text{mol/L}$)		300
BUN (mmol/L)		12

ALT=Alanine Aminotransferase; AST=Aspartate Aminotransferase; BUN=Blood urea nitrogen; ULN=Upper limit of normal

4.6.3. Potentially Clinically Important Vital Sign Values

Vital sign values are PCI if they meet either or both of the observed value criteria and the change from baseline criteria. The PCI vital sign values are presented in [Table 10](#) below.

Table 10: Potentially Clinically Important Vital Sign Criteria

Parameter	PCI Low	PCI High
Systolic Blood Pressure	≤ 90 mmHg and/or decrease ≥ 20 mmHg from baseline	≥ 180 mmHg and/or increase ≥ 20 mmHg from baseline
Diastolic Blood Pressure	≤ 50 mmHg and/or decrease ≥ 15 mmHg from baseline	≥ 105 mmHg and/or increase ≥ 15 mmHg from baseline
Pulse Rate	≤ 50 bpm and/or decrease ≥ 15 bpm from baseline	≥ 120 bpm and/or increase ≥ 15 bpm from baseline
Respiratory Rate	≤ 8 brpm and/or decrease ≥ 7 brpm from baseline	≥ 25 brpm and/or increase ≥ 7 brpm from baseline
Temperature		$\geq 38.3^{\circ}\text{C}$ and/or increase $\geq 1.1^{\circ}\text{C}$ from baseline

bpm=Beats per minute; brpm=Breaths per minute

4.6.4. Immunogenicity

Serum samples will be collected and will be tested for binding anti-AUX-I and anti-AUX-II antibodies. When immunogenicity samples are required on Day 1, the samples will be collected prior to study treatment administration. The samples also will be tested for neutralizing antibodies at times to be determined by the sponsor.

4.7. Pharmacodynamics

4.7.1. Comparison of Baseline (Screening) MRI Tissue Morphology and Septae

To radiologically assess the impact of treatment with CCH in adult females with cellulite, Baseline (Screening) MRI tissue morphology and septae will be compared to images taken at Day 71.

The long-term impact of treatment with CCH in adult females with cellulite will be assessed by comparing the changes in MRI tissue morphology and septae at Day 251 to Baseline (Screening).

4.7.2. Comparison of Baseline (Screening) Histopathology

The evaluation of tissue histopathology in assessing the impact of treatment with CCH in adult females with cellulite will be done by comparing Baseline (Screening) histopathology to the sample taken at Day 71.

The evaluation of tissue histopathology in assessing the long-term impact of treatment with CCH in adult females with cellulite will be done by comparing Baseline (Screening) histopathology to the sample taken at Day 251.

5. ANALYSIS POPULATIONS

The study will use the following analysis populations for data summarization.

Table 11: Analysis Population

Population	Definition	Displays
Safety Population	The Safety Population will include all subjects who have undergone any MRI or biopsy at Screening.	All demographic and baseline characteristics as well as safety parameters will be summarized based on this population.
Evaluable Population	The Evaluable Population will include all subjects in the Safety Population who have a baseline and at least 1 post-injection PR-PCSS evaluation.	All efficacy analyses will be based on this population.

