^a Performed prior to any study-required assessments, unless exceptions granted for standard of care procedures. A separate informed consent may be used for HIV testing and must be signed before the sample is collected, if required.

^b Should be reassessed and verified prior to dosing.

^c Vital signs will be collected up to 4 hours prior to, and at 15 and 30 minutes after, study treatment administration on Days 1, 22, and 43.

^d Urine pregnancy test should be completed prior to the MRI.

^e At screening all 4 potential treatment areas (each buttock and each thigh) will be imaged; and CR-PCSS, PR-PCSS, and Hexsel CSS assessments will be done for each potential treatment area (each buttock and each thigh).

^f Before and after marking dimples for treatment. No manipulation of the treatment area should be done prior to the “before” photographs.

^g Screening MRIs will be performed after all other screening assessments (except the biopsy) have been completed. MRIs may be repeated within the screening window as often as necessary to obtain evaluable images.

^h The Day 71 and Day 251 MRIs may be performed up to 7 days prior to the indicated visit. The MRI must be completed before the biopsy required for these visits. The Day 251/Early Termination MRI is not required for subjects who withdraw from the study (early termination). The Day 71 and Day 251 MRIs may be repeated as often as necessary to obtain an evaluable image.

Table 1: Schedule of Activities (Continued)

ⁱ The screening biopsy will be performed after all other screening assessments (including MRI) are completed. The screening biopsy will be performed at least 14 days prior to the Day 1 Treatment Visit. The investigator must examine and confirm sufficient healing of the biopsy site before dosing on Day 1. The timing of all subsequent visits will be based on the actual date that the first dose of CCH is administered.

^j The Day 71 and Day 251 imaging for efficacy, PR-PCSS, and CR-PCSS must be completed prior to the biopsy sample collection required at those visits. The Day 251/Early Termination biopsy is not required for subjects who withdraw from the study (early termination). For subjects who received less than 3 doses of CCH prior to 18 March 2020, no Day 71 or Day 251 biopsy samples will be collected.

^k Visit not required for subjects who had less than 3 doses of CCH prior to 18 March 2020.

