9.2. Populations for Analysis

For the purposes of analysis, the following populations are defined:

- The Safety Population will include all subjects who have undergone the first (screening) biopsy.
- The Evaluable Population will include all subjects in the Safety Population who received their first dose of CCH in this study after 18 March 2020 and who had a baseline and at least 1 postinjection PR-PCSS evaluation.

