9.3.3. Safety Analyses

All subjects who have undergone the first biopsy during screening will be included in the safety analyses.

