9.3.3.1. Adverse Events

AEs will be coded using MedDRA by preferred term within system organ class. The number of AEs and the number of subjects reporting AEs will be listed and summarized descriptively by body system, preferred term, severity, and causality for each treatment group. Only TEAEs (events that are new in onset or aggravated in severity following treatment) will be included in all summaries. SAEs (including death) will be summarized.

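### Protocol and SAP disagree on which adverse events and which screened subjects enter the safety summaries, and the SAP lists no severity table for treatment-emergent events

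*SAP*

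**What the plan says.** **Population.** Protocol 9.2: "The Safety Population will include all subjects who have undergone the first (screening) biopsy". Protocol 9.3.3 repeats the rule: "All subjects who have undergone the first biopsy during screening will be included in the safety analyses". SAP section 5, Table 11, is wider: "The Safety Population will include all subjects who have undergone any MRI or biopsy at Screening".

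**Scope of AE summaries.** Protocol 9.3.3.1: "Only TEAEs (events that are new in onset or aggravated in severity following treatment) will be included in all summaries". The same section asks for AEs to be "summarized descriptively by body system, preferred term, severity, and causality for each treatment group". SAP 7.7.2 says: "All AE summary tables will include TEAEs and the AEs before the first injection". Protocol section 3 makes the safety endpoint a proportion of subjects for AEs, TEAEs, AEs of special interest (AESIs) and serious AEs, each named separately.

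**Columns.** SAP 7.7 bases safety summaries on the Safety Population. SAP 7.7.2 presents AEs by region and overall. SAP 7.3 (for most variables), 7.5, 7.7.3 and 7.7.4 add a group for subjects who were not treated.

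**Timing.** Protocol 1.2, footnote i: "The screening biopsy will be performed after all other screening assessments (including MRI) are completed" and "The screening biopsy will be performed at least 14 days prior to the Day 1 Treatment Visit".

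**The concern.** A programmer cannot follow both documents. The protocol's rule removes pre-injection AEs from the summaries; the SAP's rule puts them in. The two safety sets differ for anyone who is scanned and then fails screening before biopsy.

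This bears on a stated safety endpoint. Protocol 2.3 lists bleeding, bruising and pain among the risks of punch biopsy, and names injection-site bruising, swelling and pain as the common reactions to CCH. Procedure events before any drug can therefore resemble drug events. If both go into one count, the severity and serious-event tables no longer describe what happened on CCH. If undosed subjects sit in the overall denominator, the overall percentages do not describe dosed subjects either.

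**Working it through.** No figure in the plan needs reproducing: the point rests on comparing texts, plus one illustrative calculation.

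**1. AE scope.** SAP 7.7.2 lists 12 SOC/PT tables. Six are titled TEAE: relationship; related serious; leading to drug interruption or discontinuation; related leading to the same; related leading to withdrawal; related resulting in death. Six are not: all AEs, severity, serious, withdrawal, death, AESIs.
- Literal reading of the SAP sentence: all 12 tables and the overall summary take in pre-injection AEs.
- Narrowest reading (tables titled TEAE stay TEAE-only): 6 of 12, plus the overall summary.

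Both readings conflict with protocol 9.3.3.1. That section also sits badly with protocol section 3, whose endpoint counts AEs as well as TEAEs, so the SAP is not the only text that needs attention.

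**2. Population.** Both definitions admit a subject who is biopsied and never dosed. They differ only for a subject with an MRI and no biopsy. That subject is foreseeable: the biopsy follows the MRI (footnote i), evaluable images are an entry criterion (protocol 5.1, item 13), and failing to get them is a named reason for screen failure (protocol 5.4).

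**3. Denominator.** SAP 6.1 gives two rules: the number in the population, and the number with non-missing values. A subject with no AE does not have a missing value (my inference), so neither rule removes undosed subjects from the overall AE column.

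Illustration: let *u* be the number of undosed subjects in the Safety Population. The documents do not give it. With about 19 dosed (protocol 4.1), a PT reported by one subject has an overall percentage of 1/(19 + *u*):

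| *u* | Calculation | Result | Meets the 5% cut for common non-serious AEs? |
|---|---|---|---|
| 0 | 1/19 | 5.3% | yes |
| 1 | 1/20 | 5.0% | yes |
| 2 | 1/21 | 4.8% | no |
| 3 | 1/22 | 4.5% | no |

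Here *u* counts all undosed subjects, including biopsied ones whom both documents admit. The table shows the effect of the missing column, not of the population conflict alone.

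**4. Missing outputs.** The overall summary has 12 lines, none for TEAEs. There is no SOC/PT table of all TEAEs. The only severity table is *AEs by Severity*. Protocol 9.3.3.1 requires severity and allows only TEAEs, so the table it calls for is not on the SAP's list.

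**5. Pre-dose events.** Every dosed subject should have at least 14 days between screening biopsy and Day 1. AEs are collected from consent (protocol 8.3.1), and the biopsy site is examined on Day 1. Pre-injection AEs are thus to be expected even if *u* = 0.

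**The case against.** The best defence is that this is a small descriptive study and little is lost. TEAE incidence by PT can be rebuilt from *TEAEs by Relationship to Study Drug* and the number treated. TEAE severity can be recovered for about 19 subjects from the AE listing and the derived onset day. A PT that misses the 5% cut still appears in *All AEs*. The SAP's wider AE scope also serves the endpoint in protocol section 3 better than protocol 9.3.3.1 does. All of this stands and limits the consequences. It does not remove the contradictions, and an endpoint should not have to be assembled from listings.

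Some stronger readings are tempting, and the documents do not support them:
- **Pooling is certain.** The SAP says the tables include both kinds of event. The layouts are in SAP Module 2, which was not supplied and may show them separately.
- **SAP section 8 wrongly fails to declare departures.** The SAP was written to the original protocol and Amendment 1. Without that text, no omission can be shown.
- **AEs in MRI-only subjects go uncollected.** Protocol 5.4 requires AEs to be recorded for all screen failures, and 8.3.1 starts collection at consent. Only the end of their follow-up is unstated.
- **At most about 6 subjects are undosed.** The SAP's plan of about 18 screened and 12 dosed is an approximate plan for a smaller study and does not bound the 19-dosed design.
- **A pre-dose biopsy bruise becomes an AESI.** The AESI definition ties bruising to the site of drug administration, which does not exist before Day 1.
- **The missing column is a deliberate AE choice.** SAP 7.3 also omits the untreated group for age, height, weight and BMI, so loose drafting is as likely.

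**Conclusion.** The point holds on the text. Protocol and SAP conflict on AE scope and on the Safety Population; the AE tables leave undosed subjects in the overall denominator; and the SAP lists no table of all TEAEs, no TEAE severity table and no overall TEAE line. At minimum, the overall summary and 6 of 12 SOC/PT tables depart from protocol 9.3.3.1.

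The numerical size is unknown. It depends on how many undosed subjects enter the set and how many pre-dose events occur. Undosed subjects lower overall percentages and pre-dose events raise counts, so no net direction can be claimed. A reader might infer that the region columns are diluted too. Region is selected at screening, but the SAP does not say whether undosed subjects are placed under a region, so this is not shown. Combining pre-dose with on-drug events in the severity and serious tables is what would follow unless the Module 2 layouts separate them; the missing column and tables are likewise shown for Module 1 only.

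This should be corrected before the tables are produced. It is a reporting defect in a descriptive study, not a threat to its design.

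**What to change.** - Use one Safety Population definition in protocol 9.2 and 9.3.3 and SAP Table 11. If MRI-only subjects are kept, state when their AE follow-up ends.
- Reconcile protocol 9.3.3.1 with the endpoint in protocol section 3 and with SAP 7.7.2.
- In SAP 7.7.2 add a table of all TEAEs by SOC and PT, a table of TEAEs by severity, and an overall-summary line for any TEAE. Use subjects with at least 1 CCH dose as the denominator, and base the 5% threshold on the same subjects.
- In the all-AE, severity, serious, withdrawal, death and AESI tables, add a not-treated column and show pre-injection events apart from TEAEs. Do not drop pre-dose AESIs: hypersensitivity reactions are AESIs without reference to the injection site, allergy to the biopsy anaesthetic is a stated risk, and the endpoint counts each AESI.

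The cost is two tables, one summary line, a few SAP sentences and matching protocol wording through the usual amendment approval. No new data are needed. The limit of the repair should be stated: the Day 71 and Day 251 biopsies come after CCH, so their events remain TEAEs. It separates pre-dose from post-dose events, not all biopsy effects from drug effects.
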